1.0 Introduction and Background

Bone metastases are not only the most common cause of cancer-related pain, but palliative radiotherapy is prescribed most frequently to relieve symptoms. External beam radiotherapy (EBRT) is a well-established and efficacious method of palliating painful bone metastases (1). Numerous randomized trials have evaluated the potential benefits of certain dose fractionations of EBRT (1-7), yet controversy remains over the optimal treatment schedule. For example, RTOG 97-14 randomized 898 patients with breast or prostate cancer to receive 8 Gy in 1 fraction or 30 Gy in 10 fractions. There was no significant difference in complete or partial pain relief at 3 months. Patients in the single dose group had a significantly higher retreatment rate at 3 months (18% vs. 9%) but a statistically lower toxicity rate (10% vs 17%) (8). An economic analysis of this trial calculated quality-adjusted life year survival to be 7.3 months vs 9.5 months in the two treatment arms. The authors concluded that single fraction was less expensive and more cost-effective (9). Chow et al conducted a systematic review and meta-analysis of randomized palliative radiotherapy trials comparing single fractions to multiple fractions. Twenty-five randomized trials were identified with no significant differences in pain response rates. The likelihood of re-treatment was 2.6-fold higher (95% CI, 1.92-3.47; $P < 0.00001$) in single fraction EBRT arm patients (10).

1.1 Rationale for Proposed Treatment Dose and Schedule

The protocol attempts to further define the results of RTOG 97-14, which demonstrated that 8 Gy x 1 was equal to 30 Gy in 10 fractions for the majority of clinical endpoints. The primary exception was the rate of retreatment, where 8 Gy x1 was shown to require additional therapy. In this study, we are investigating if a second fraction given within 7 days of the first fraction, reduces the retreatment rate or improves pain control.

2.0 Objectives

2.1 Primary Objective

- 2.1.1 To determine whether 8 Gy x 2 fractions results in lower cumulative re-treatment rates at 6 months post-treatment completion compared to 8 Gy x 1 fraction in solid tumor patients with bone metastases.

2.2 Secondary Objectives

- 2.2.1 To determine whether 8 Gy x 2 fractions provides superior pain at 3 and 6 months post-treatment completion compared to 8 Gy x 1 fraction in solid tumor patients with bone metastases.
- 2.2.2 To determine whether 8 Gy x 2 fractions is associated with improved quality of life at 3 and 6 months post-treatment completion compared to 8 Gy x 1 fraction in solid tumor patients with bone metastases.
- 2.2.3 To determine if 8 Gy x 2 fractions is associated with increased toxicity.
- 2.2.4 To correlate patient satisfaction, perceived stress, and social support assessed via self-reported outcomes with treatment outcomes.

2.3 Exploratory Objective

- 2.3.1 To determine whether use of a bone strengthening agent is associated with improved pain relief, decreased narcotic usage, and re-treatment rates.
- 2.3.2 To assess the impact of pain response after radiotherapy on bone structural properties such as bone mineral density and cortical thickness

3.0 Patient Selection

3.1 Inclusion Criteria

- 3.1.1 Diagnosis of cancer, not including multiple myeloma or lymphoma/leukemia.
- 3.1.2 Radiographic evidence* of bone metastases within 8 weeks of study for non-weight bearing sites and 4 weeks for weight bearing sites. The patient must have pain which appears to be related to the radiographically documented metastasis in the opinion of the treating physician, and the decision has been made by the responsible clinician that a course of palliative external beam radiation therapy is appropriate treatment. Multiple sites eligible if they can be included in no greater than 3 treatment sites and not all identifiable lesions will require treatment unless they are painful lesions

*This should be one of the following: Plain Film, Bone Scan, PET scan, CT scan, or MRI.

- 3.1.3 The involved bone(s) is/are orthopedically stable and not in need of stabilization via either definitive RT, surgical intervention, or both.

- 3.1.4 Eligible Treatment Sites Are:

Weight bearing sites

1. pelvis (*excluding pubis*)
2. femur
3. sacrum and/or sacroiliac joints
4. tibia
5. up to 5 consecutive cervical, thoracic or lumbar vertebral bodies
6. lumbosacral spine

Non-weight bearing sites

7. up to 3 consecutive ribs
8. humerus
9. fibula
10. radius ± ulna
11. clavicle
12. sternum
13. scapula
14. pubis
15. skull
16. bones of hands or feet

If multiple sites are treated, the treatment site is included as weight-bearing if any of the sites include the pelvis, sacrum, femur or tibia.

- 3.1.5 Pain score of at ≥ 5 on a scale of 0 – 10 within a week of enrollment OR pain score < 5 with ≥ 60 mg of morphine (or equivalent) per day.
- 3.1.6 ECOG performance status of 0 - 3.
- 3.1.7 Ability to understand and the willingness to sign an IRB-approved informed consent document.
- 3.1.8 Negative pregnancy test at study registration.
- 3.1.9 Life expectancy of at least 12 weeks as deemed by the treating oncologist.
- 3.1.10 Patients will be eligible for treatment of multiple synchronous osseous sites only if those sites can be included in no more than three treatment sites. For patients with painful metastases that are contiguous but do not fit into the definition of a site listed above, those patients will still be eligible but will be considered to have two treatment sites. For example, a patient with a lesion of T4, T7 and T9 would be eligible but would be considered as two treatment sites since more than five consecutive vertebral bodies would be treated. These lesions could be treated with one field, even though the treatment is coded as two sites.

3.2 Exclusion Criteria

- 3.2.1 Previous radiotherapy or palliative surgery to the painful site that is planned for treatment.
- 3.2.2 Spinal cord or cauda equine compression/effacement in vertebral metastases with neurological symptoms other than just pain for the lesion that is planned for treatment.

3.3 Inclusion of Women and Minorities

Men and women of all races and ethnicities who meet the above-described eligibility criteria are eligible to participate in this study.

The study consent form will also be provided in Spanish for Spanish-speaking participants. Based on CCCWFU population estimates, we expect approximately 40% of participants to be women. Translating this to our sample size estimate of 158, we plan to enroll at least 63 women.

We do not expect the percentage of Hispanic/Latino or racial minority cancer patients eligible for this study to be higher than the percentage of Hispanic or racial minority new cancer patients seen at CCCWFU (2.2% and 13.3%, respectively); therefore, we plan to enroll at least 21 racial minority and 3 Hispanic/Latino patients.

Should we not meet or exceed these estimates, the PI will engage the Cancer Center Health Equity Advisory Group to discuss strategies to enhance recruitment in these target populations.

4.0 Methods

4.1 Study Design

We will use a prospective randomized study design for recruiting patients with painful bone metastasis at the CCCWFU. Pain will be assessed prior to randomization. Patients will be randomized between 1 or 2 fractions of 8 Gy. The randomization will occur after registration; patients will be randomized equally between the two treatment arms. Treatment needs to begin within 14 days of registration. All baseline data needs to be collected before treatment. Quality control, such as valid values, range checks and between-variable consistency will be performed at time of data entry. Data will be kept secure with password protection.

4.2 Registration Procedures

All patients entered on any CCCWFU trial, whether treatment, companion, or cancer control trial, **must** be registered with the CCCWFU Protocol Registrar or entered into ORIS Screening Log within 24 hours of Informed Consent. Patients **must** be registered prior to the initiation of treatment.

You must perform the following steps in order to ensure prompt registration of your patient:

1. Complete the Eligibility Checklist (Appendix B)
2. Complete the Protocol Registration Form (Appendix A)
3. Alert the Cancer Center registrar by phone, *and then* send the signed Informed Consent Form, Eligibility Checklist and Protocol Registration Form to the registrar, either by fax or e-mail.

Contact Information:

Protocol Registrar [REDACTED]
Protocol Registrar [contact]
Protocol Registrar E-MAIL ([contact])

*Protocol Registration is open from 8:30 AM – 4:00 PM, Monday-Friday.

4. Fax/e-mail ALL eligibility source documents with registration. Patients **will not** be registered without all required supporting documents.

Note: If labs were performed at an outside institution, provide a printout of the results. Ensure that the most recent lab values are sent.

To complete the registration process, the Registrar will:

- assign a patient study number
- randomize the patient
- register the patient on the study

4.3 Data Collection

At the time of enrollment, a detailed history and physical exam will be performed, including abstraction of patient vital signs and also documenting co-morbidities, patient demographics, age, gender, other medical conditions, and tumor characteristics. Other variables, such as education level, type of health insurance, and marital status (married/single/widowed/divorced/other) will also be obtained.

Blood Collection: Patients may consent to provide optional blood samples to be used for future genomic studies at baseline.

Prior Cancer Therapy: Information regarding the patient's history for anti-cancer therapy will be recorded.

Use of Bisphosphonates/Denosumab: Information regarding the patient's history for the use of bisphosphonates will be recorded. This will include the specific agent, dose, and date treatment started.

Changes in systemic chemotherapy, hormonal therapy, immunotherapy or the use of bisphosphonates for 4 weeks before and after the delivery of radiotherapy are allowed and will be recorded.

Pain level and Pain Medications: The patient's pain level will be assessed using the NRPS (detailed below). Information regarding the patient's history for the use of pain medications will be recorded. This will include the specific agent, dose, and date treatment started.

Nutrition Status, vitals, BMI: At each encounter, height (at baseline only), weight, Body Mass Index (BMI=kg/M²), and history of weight loss within three months prior to enrollment until patient's study completion will be recorded and/or extracted from patient records.

ECOG Performance Status

Patient Self-Reported Outcomes (SRO):

For evaluation of pain relief, the Numerical Rating Pain Scale (NRPS; Jensen 1999) will be used. The NRPS is a simple measure of pain on an 11-point scale (0-10). In the study comparing the reliability and validity of several measures of pain intensity, the composites of 0-10 ratings have been shown to be useful when maximal reliability was necessary in studies with relatively small sample sizes or in clinical settings in which monitoring of changes in pain intensity in individuals is needed. This will be performed prior to treatment and again at 1, 2, 3, and 6 months.

For patients with a pain score >4 in the treated area at the 3 and 6 month follow-up, imaging (plain film, CT, bone scan, MRI) is recommended to assess for bone stability and pathologic fractures. Imaging should correlate with other imaging ordered by other treating physicians when possible. Coordination of all treatment and imaging should be collaborative to ease patient burden.

We will also include the following psychosocial measures at baseline and again at 3 and 6 months:

- European Organization for Research and Treatment of Cancer (EORTC) QLQ-C15-PAL
- Patient Satisfaction with Cancer Care (11)
- Perceived Stress Scale (12)
- Social Support (13)

Measurement of Treatment-Related Toxicities: Adverse events will be evaluated by the NCI Common Terminology Criteria for Adverse Event (CTCAE), v. 4.0. (14). Because of the patient population as well as the treatment, emphasis will be placed on gastrointestinal (GI disturbance, esophagitis, diarrhea, nausea, and vomiting), hematological (low blood counts or bleeding), spinal (bone fracture, compression fracture, insufficiency, or myelitis), and pulmonary toxicities (pneumonitis). However, all adverse events recorded by clinical research coordinators will be analyzed. Given the variety of non-protocol related treatment, toxicity will be assessed at 30 days after protocol treatment, as per DSMC requirements. These will be documented in Appendix I.

Focused Late AE Assessments: At 2, 3 and 6 months post-treatment, a focused AE assessment dependent upon the specific body area treated will be performed. These will be documented in Appendix I. Specific AEs to be collected will include the following:

- a) Fistula formation
 - a. Abnormal opening in the passageway from mouth to stomach (esophagus), bowels or bladder
- b) Scarring of the small or large bowel resulting in a blockage in the bowel that would require treatment
- c) Fracture of the bone within the radiotherapy treatment field (Fractures may require surgical treatment to prevent permanent disability).
- d) Temporary or permanent damage to the spinal cord, resulting in:
 - a. Skin sensations, such as burning, prickling, itching, or tingling
 - b. Muscle weakness causing inability to walk (paralysis)
 - c. Decreased ability or loss of ability to move a body part or to hold urine or control a bowel movement

Imaging: The patient will undergo CT-Simulation prior to treatment. If deemed necessary by the treating physician at the time, follow-up imaging is allowed at 3- and 6-months after treatment. These scans, if performed, will be as part of standard of care, particularly in the setting of increased pain at post-treatment evaluations (see above). Imaging data obtained from these scans will be collected for the purposes of the exploratory objective (Section 2.3).

4.4 Radiation Therapy

4.4.1 Treatment Plan

Arm 1: 8.0 Gy x 1 fraction.

Arm 2: 8.0 Gy x 2 fractions to 16.0 Gy total dose with 3-7 days in between.

- 4.4.2 Patient Positioning and Simulation: Patients must be positioned in a stable supine or prone position at the treating physician's discretion. Any immobilization techniques can be used for 3D conformal therapy at the treating physician's discretion. For cervical spine or cervicothoracic junctional areas, a head and neck immobilization device is preferred. Simulation of treatment fields is required prior to the treatment.
- 4.4.4 3D Treatment CT simulation is required. Non-coplanar beams can be employed. Multiple beam directions can be used. Target volume should be covered by more than or equal to 90% of the prescription dose.
- 4.4.5 Simulation of treatment fields is required prior to the first treatment. Prior to the first treatment, there must be an approved simulation or portal film documenting that the treatment site is adequately covered and approved by a radiation oncologist.
- 4.4.6 Treatment machine requirements. Treatment must be given using megavoltage equipment with 4-20 MV photons or 5-20 MeV electrons. The minimum Source-Axis Distance (SAD) shall be 80 cm.
- 4.4.7 For spine lesions, treatment volume will include the entire vertebral body(s) of the involved spine, plus one vertebral body superior and one vertebral body inferior to the index spine. A treatment field margin of 1-2 cm laterally beyond the vertebral body(s) can be used based on the treating physician's discretion. For non-spine lesion, treatment volume will generally include the lesion as identified on imaging studies with 1-2 cm margin. Final treatment volume will be at treating physician's discretion.
- 4.4.8 Rib metastases may be treated with electrons or with photons. When electrons are used, the appropriate energy should be chosen such that the entire lesion is covered by the 90% (or higher) isodose curve. The dose will be prescribed to the 100% isodose line.

When photons are used, parallel opposed fields may be used, with the depth prescribed to the mid thickness. Oblique/tangential fields for rib metastasis are strongly encouraged to avoid treatment of underlying structures. A single field may be used to cover the lesion, with the depth set at the estimated depth of the rib lesion, and the dose prescribed to that level.

- 4.4.9 When more than one osseous site is to be included into one treatment field, the treating radiation oncologist may use differing field arrangements at her/his discretion, with the fields arranged to provide relatively uniform treatment of the target sites with a minimum of uninvolved normal tissues.
- 4.4.10 For patients who receiving 8 Gy x 2 to an area near or involving either the spinal cord or cauda equina, the spinal cord and cauda equina needs to be contoured. The dose to the countered cord/cauda equina this this region will be limited to 107% of the prescribed dose. If needed, the PTV coverage can be lowered to 85%. If PTV coverage is between 85% and 80%, a minor deviation should be reported. If PTV coverage is below 80%, a major deviation should be reported.

5.0 Study Outcomes and Study Measures

5.1 Primary Outcome

- 5.1.1 Cumulative re-treatment rates by treatment arm assessed at 6 months post-treatment completion.

5.2 Secondary Outcomes

- 5.2.1 Pain, on a 0-10 scale, and narcotic use, in daily oral morphine equivalents, by treatment arm assessed at 3 and 6 months post-treatment completion.
- 5.2.2 Quality of life by treatment arm, assessed by QLQ-C15-PAL at 3 and 6 months post-treatment completion.
- 5.2.3 Toxicity by treatment arm, assessed by CTCAE version 4.0.
- 5.2.4 Association between patient satisfaction, perceived stress, and social support assessed via self-reported surveys and treatment outcomes.

5.3 Exploratory Outcome

- 5.3.1 Association of use of a bone strengthening agent with improved pain relief, decreased narcotic usage, and re-treatment rates.
- 5.3.2 Association of pain response after radiotherapy on bone structural properties such as bone mineral density and cortical thickness.

6.0 Treatment Plan

6.1 Study-Related Activities

	Screening/ Baseline ^a	Pre-Treatment ^h	At Each Treatment	1 Month Post Treatment Completion ^{f,g}	2 Months Post Treatment Completion ^{f,g}	3 Months Post- Treatment Completion ^{f,g}	6 Months Post- Treatment Completion ^{f,g}
Informed Consent	X						
Demographics: age, gender, education, health, insurance, marital status	X						
Medical history, tumor characteristics	X						
Performance Status (ECOG)	X					X	X
B-HCG ^b	X						
Blood Collection (optional)		X				X ^{f,i}	
Nutritional status, BMI _i	X		X			X	X
Vital Signs	X					X	X
Radiologic assessment	X ^c					X ^{e,m}	X ^{e,m}
Patient Questionnaires ^d		X				X	X
Concomitant Medications	X		X	X	X ^k	X ^k	X ^k
Adverse event evaluation			X	X	X ^j	X ^j	X ^j
NRPS Pain Scale	X			X ^g	X ^g	X ^g	X ^g

a. Pre-study requirements listed in table must be completed **within** 14 days prior to registration unless otherwise noted.

b. Serum pregnancy test (women of childbearing potential).

c. Within 8 weeks of registration for non-weight bearing sites and 4 weeks for weight bearing sites

d. See Appendix G.

e. Imaging ordered by the treating physician according to the standard of care, only if indicated. CT scan is not required to be performed for study purposes at follow up, but any CT scans obtained as standard of care will be used for purposes of reviewing changes in cortical thickness as an exploratory aim.

f. To be completed 3-6 weeks from final treatment date (1 month visit), 7-9 weeks from final treatment date (2 month visit), 10-18 weeks from final treatment date (3 month visit) and 20-34 weeks from final treatment date (6 month visit).

g. For patients who are undergoing additional therapy of any kind and are being followed by another treating physician, the follow-up visit can be deferred to that treating physician. Schedule of follow-up may be deferred to that treating physician and activities will be captured when they fall within visit windows. Toxicity (AEs), pain (NRPS), and patient questionnaire can be done over the phone +/- 5 days of said visit.

h. To be completed any time after consent is signed, but prior to treatment. Not needed for registration.

i. Height will be captured at the Pre-Study/Baseline visit only.

j. Focused AE assessment according to those specified in Section 4.3 and outlined in Appendix I (2-, 3- and 6- month assessment).
 k. Focused ConMed assessment; collected medications related to bone pain and bone-strengthening agents only
 (bisphosphonates, RANK-L inhibitors, parathyroid hormone analogs/modulators/agonists).

l. Optional blood collection for follow-up must occur at 3 months if consented to by the subject (See Section 9.0).

m. Appendix K to be completed at the time of Data Reconciliation.

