11.2 Analysis of Secondary Objective

There are several secondary outcomes of interest in this study. Most of these are measured on a continuous scale (i.e., quality of life by QLQ-C15-PAL, Patient satisfaction with cancer care, perceived stress scale) and thus will be compared between groups using 2-sample t-tests. In addition, the variable for pain response is categorical rather than continuous and will be compared at 3-months between groups using a Fisher's exact test. Patients categorized as Complete or Partial Responders will be compared with those categorized as stable or worsening pain responders.

Groups will also be compared to determine whether there are any differences in the number or severity of toxicities. When comparing severity of toxicities between groups, chi-square tests will be examined. The Cochran-Armitage trend test (in SAS Proc Freq) can be used to determine if there is evidence a trend in severity of toxicities when comparing groups.

In addition to the primary and secondary analyses described above, analyses will be performed that examine whether there are associations between quality of life, patient satisfaction and perceived stress measures and treatment outcome (re-treatment rates or amount of pain relief). In these

analyses, the outcome will be either re-treatment (yes/no) or amount of pain and predictors will include treatment arm, patient level measure and the treatment by patient level measure (i.e., QLQ-C15-PAL) interaction. For these analyses, either multiple logistic regression (for binary outcomes) models or analysis of covariance (ANCOVA) models for continuous outcomes will be used.

In these multiple logistic regression or ANCOVA models additional characteristics such as gender, whether the patient has weight-bearing (yes/no), ECOG performance status, number of lesions, or biophosphonates will also be considered as covariates in the models.

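### Footnote h in protocol section 6.1 lets the baseline questionnaires be completed after randomisation to visibly different arms, so any analysis that uses those baseline scores may be using post-allocation data

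*Combined protocol and SAP*

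**What the plan says.** Protocol section 4.1 puts randomisation after registration: "The randomization will occur after registration; patients will be randomized equally between the two treatment arms". Section 4.2 lists "randomize the patient" among the registrar's steps in completing registration. Section 4.1 then allows a gap before radiotherapy: "Treatment needs to begin within 14 days of registration".

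For baseline data in general, section 4.1 sets the deadline at treatment: "All baseline data needs to be collected before treatment". Pain has a stricter rule in the same section: "Pain will be assessed prior to randomization".

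In the section 6.1 table, the pain scale is in the screening/baseline column, which footnote a ties to the period before registration. The first Appendix G questionnaire is in the separate pre-treatment column, under footnote h: "To be completed any time after consent is signed, but prior to treatment. Not needed for registration".

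Section 4.3 treats the four instruments in Appendix G as baseline measures repeated at 3 and 6 months. Section 11.2 plans regression models for re-treatment or amount of pain in which "predictors will include treatment arm, patient level measure and the treatment by patient level measure" interaction. It does not say at which time point the patient-level measure is taken.

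**The concern.** A baseline score is useful because allocation cannot have affected it. Here the rule allows a patient to learn whether they will have one fraction or two, and then complete a form that is filed as baseline. The arms differ visibly, by one treatment visit or two visits 3 to 7 days apart. The documents describe no blinding, sham fraction or delayed disclosure.

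Some of the items could respond to that knowledge. The satisfaction scale asks about involvement in decisions and about receiving the services needed, and the stress scale asks about control. If answers move after allocation, and move differently in the two arms, the score is partly an effect of the arm. Entering it beside the arm as a predictor, or subtracting it from a follow-up score, would then mix the two. Objective 2.2.4 and any baseline-adjusted look at quality of life would be exposed.

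**Working it through.** **1. The permitted window.** Take registration as day 0.

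| Event | Timing | Source |
|---|---|---|
| Consent | before day 0 | Appendix A |
| Pain score (NRPS) | before randomisation | 4.1; 6.1 table |
| Randomisation | at or just after day 0 | 4.1, 4.2 |
| First fraction | day 14 at the latest | 4.1 |
| Baseline Appendix G | from consent to just before the first fraction | 6.1, footnote h |

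The part of the questionnaire window that follows randomisation runs from 0 to about 14 days. These 14 days come from the registration-to-treatment limit in section 4.1. They are not the 14 days before registration in footnote a. The registration steps in section 4.2 and the eligibility checklist in Appendix B do not ask for the questionnaire, so nothing else closes the window.

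**2. Which analyses use the baseline score.**

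| Analysis | Uses baseline Appendix G? |
|---|---|
| Re-treatment, log-rank test (11.1) | No |
| Pain response, Fisher's exact test (11.2) | No |
| Toxicity comparisons (11.2) | No |
| Quality of life at 3 and 6 months, t-test (5.2.2, 11.2) | No; no baseline covariate or change score is specified |
| Logistic or ANCOVA models with arm, measure and interaction (11.2) | Possibly; time point not stated |
| Any later change-score or baseline-adjusted analysis | Yes |

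**3. What a shift would do in the section 11.2 models.** Let the outcome (or the log-odds of re-treatment) in arm g be α_g + β_g·X, where X is the score before allocation is known. Suppose knowing the arm moves everyone in arm g by d_g, so that the recorded score is X* = X + d_g. Assume that the shift does not itself carry through to the outcome. Substituting X = X* − d_g gives

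α_g + β_g·(X* − d_g) = (α_g − β_g·d_g) + β_g·X*.

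- Each within-arm slope is still β_g, so the association and the arm-by-measure interaction β_2 − β_1 do not change.
- At any fixed X*, the arm difference moves by −(β_2·d_2 − β_1·d_1). With a common slope β this is −β·(d_2 − d_1).
- In a change-score comparison, the arm difference moves by −(d_2 − d_1).

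**4. When the slopes also move.** They change only if the shift varies between patients. Two examples:

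- If the shift grows with the score, X* = X·(1 + k_g), the slope becomes β_g/(1 + k_g). The interaction is then distorted if k_1 and k_2 differ.
- If a fraction p of an arm answers late and shifts by d (in within-arm SDs), with lateness unrelated to the score, the mean shift is p·d. The slope is multiplied by 1/(1 + p(1−p)d²). Since p(1−p) is at most 0.25, an assumed d of 0.3 gives a factor no lower than 1/(1 + 0.25 × 0.09) = 1/1.0225 = 0.978, about 2% weaker.

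**5. Scale.** The documents give no value for d, β, p or the day on which patients learn their arm. As an assumption only, a net shift d_2 − d_1 of 0.1 to 0.3 SD in fully late-collected data would move a change-score arm difference by 0.1 to 0.3 SD, and the arm term in the models by 0.1β to 0.3β (β per SD). If no questionnaire is completed after allocation, every one of these is zero.

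**The case against.** The strongest reply is that the plan as written hardly relies on the baseline scores. Quality of life by arm is an unadjusted comparison of follow-up scores, and a disturbed baseline cannot bias it. A reader might infer that objective 2.2.2 is biased; sections 5.2.2 and 11.2 do not support that. Objective 2.2.4 asks about associations, and under a uniform shift these and the interaction survive. Only the arm term moves, and it is not the planned test of the arms for re-treatment or pain response. All of this stands.

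A reader might also attach a size by multiplying an assumed shift by a baseline-to-follow-up correlation. That product describes an ANCOVA of follow-up quality of life on baseline quality of life. Section 11.2 specifies no such model: its regression outcomes are re-treatment and pain.

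The instruments offer some protection. The stress items look back a month, and the support items describe a standing network. But most of the quality-of-life items look back a week, and the satisfaction section is introduced with the same period. A form completed on day 14 would have a one-week recall lying wholly after randomisation, and about half of a one-month recall would do so. The protection is partial.

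Finally, footnote h is probably a deliberate allowance. Appendix G has 15 + 10 + 12 + 18 = 55 items, for patients in considerable pain or on substantial opioid doses, with ECOG status up to 3. That is a fair reason not to make the form a barrier to registration, and it is why the fix includes a lighter option.

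**Conclusion.** The point holds as a permitted possibility. A stated rule, not a missing detail, allows a form labelled baseline to be completed up to about 14 days after allocation in a trial whose arms patients can tell apart. The protocol already applies the safer order to pain and gives no reason for treating the other patient-reported measures differently. It would be wrong to say that pain is the only item due before randomisation: ECOG status, vital signs, history and other screening items are too. The contrast holds only among patient-reported measures.

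The conclusion rests on two inferences: that patients learn their arm before treatment, and that the section 11.2 models or a later adjusted analysis will use the baseline score. If both are true, the arm term in those analyses may be biased, and the association or interaction may be biased where the shift is uneven. The documents do not allow the size to be computed, nor do they show that any patient answered late. This is a cheap improvement; it does not threaten the trial's main conclusions.

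**What to change.** - In the section 6.1 table, move the baseline Appendix G entry to the screening/baseline column. Amend footnote h so that the form is completed after consent and before the registrar randomises. If that is too heavy for some patients, require it at least before the patient is told the arm. The optional blood draw can stay under footnote h.
- Align the general sentence on baseline data in section 4.1 with this.
- Record the completion date of the form relative to randomisation.
- State in section 11.2 which time point supplies the patient-level measure.
- For patients already enrolled, compare the two dates, flag questionnaires completed after randomisation, and report their number by arm. Dropping those patients from the models is less attractive: it selects on something that happened after randomisation, and it costs sample size.

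The cost is one table cell, a reworded footnote, two sentences and one date field. The downside is that a few registrations may be slightly delayed while the form is finished. Forms already completed after allocation cannot be replaced, so the change helps only future enrolment.
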